1. BACKGROUND AND RATIONALE

1.1 Background

aH5N1 is a pandemic⁴ vaccine for prophylaxis of avian H5N1 influenza. aH5N1 is an inactivated, surface antigen, A/H5N1 Influenza (flu) Vaccine, with International Nonproprietary Name (INN) Pandemic Influenza Vaccine H5N1 (surface antigen, inactivated, adjuvanted), produced in embryonated hen eggs and formulated with MF59C.1 adjuvant (MF59). For clarity, the term aH5N1 will be used in the remainder of this document to refer to Pandemic Influenza Vaccine H5N1 (surface antigen, inactivated, adjuvanted).

Nonclinical studies assessed the immunogenicity (mice, rabbits, ferrets), efficacy (mice, ferrets), and toxicity (rabbits) of aH5N1 formulations. In these studies, vaccine formulations were immunogenic and protective, and there was no evidence of local or systemic toxicity. In rabbits, vaccination did not cause maternal or embryofetal toxicity, was not teratogenic, and had no effects on post-natal development. These studies support the clinical use of aH5N1.

Inactivated influenza vaccines from the applicant, including aH5N1 and aH1N1, are manufactured from the same manufacturing process but differ only in terms of antigen and adjuvant content. These vaccines are based on replication, inactivation, and purification of proteins from selected influenza viruses and each is formulated with MF59 adjuvant, which allows for administration of lower antigen doses. HA and neuraminidase (NA) proteins are included in all three vaccines. The mechanism of action of inactivated influenza vaccines is based on induction of antibodies against the purified viral HA. Production of antibodies to HA is thought to prevent viral attachment to human respiratory epithelial cells. Although there is no established correlate of protection against pandemic influenza strains, HI antibody levels have been regarded as both a sign of vaccine activity and post-vaccination HI titer $\geq 1:40$ has been associated with protection against seasonal influenza in adults.

Influenza antigen doses used to immunize against seasonal influenza have been well established for inactivated influenza vaccines (15 μ g HA per influenza strain per dose in individuals 3 to 18 years of age, and 7.5 μ g HA per influenza strain per dose in individuals 6 to <36 months of age, for most inactivated influenza vaccines).

⁴ Throughout this study protocol 'pandemic' vaccine is used for the aH5N1 vaccine, however this study is also in support of the corresponding zoonotic vaccine.

However recent experience with pandemic influenza strains has indicated that different pandemic influenza strains may require different amounts of antigen to achieve similar antibody responses. Experiences with non-adjuvanted pandemic influenza strains in adults have demonstrated that two separate doses of 90 µg HA of A/H5N1 are necessary to achieve 4-fold increases in antibodies in just over 50% of adult subjects ([Treanor 2006](#)).

During the A(H1N1)pdm09 influenza pandemic, a dose-ranging trials in adults (including elderly) and children was performed as soon as formulations were available. Ultimately, these trials established that the addition of MF59 adjuvant to A(H1N1)pdm2009 antigen allowed for administration of lower doses of antigen (7.5 µg, dose of Focetria) to achieve high seroconversion rates by HI and MN assay. Moderate seroconversion rates were also observed with even lower antigen doses (3.75 µg) when MF59 adjuvant was added (60% by HI assay). Seroconversion rates were also high in children after a single dose of 3.75 µg HA A(H1N1)pdm09 with 0.125 mL MF59 dose: 91%, 97%, 95%, and 91% in children ages 6 to 11 months, 12 to 35 months, 3 to 8 years, and 9 to 17 years, respectively.

A clinical study with still another pandemic influenza strain (A/H7N9) demonstrated that 15 µg HA antigen with 0.25 mL MF59 dose given as 2 doses was needed to achieve HI titers \geq 1:40 in adults ([Bart 2014](#)).

These experiences illustrate that for novel influenza strains, a range of doses may need to be evaluated in order to understand how much antigen and adjuvant is needed to demonstrate desirable antibody levels, and children may not demonstrate the same responses as adults to the doses given.

1.2 Rationale

The present study is a post authorization commitment in Europe. The purpose of this study is to provide additional clinical data on aH5N1 in children in anticipation of an avian influenza pandemic, as agreed in the pediatric investigational plan with EMA/Pediatric Committee. This is a pediatric dose-ranging study for aH5N1 to dosages with decreased content of HA antigen and/or MF59 adjuvant (versus the licensed dosage for adults). The study is designed to evaluate the safety and immunogenicity of two vaccinations using three different amounts of aH5N1 and two different dosages of MF59 adjuvant, administered 3 weeks apart.

The study will be conducted according to the protocol and in compliance with Good Clinical Practice, as defined by the International Council on Harmonisation, the principles outlined in the Declaration of Helsinki and all applicable federal and local regulations.

1.3 Potential Risks and Benefits

Based upon clinical studies with the aH5N1 vaccine, the following local and systemic adverse events may occur after vaccination:

Immediate hypersensitivity type reactions including anaphylaxis.

Vaccination-related anxiety symptoms such as syncope and pre-syncope.

Local reactions: erythema, induration, and pain at the injection site.

Systemic reactions: fever, (defined as body temperature $\geq 38.0^{\circ}\text{C}$), shivering (chills), irritability, diarrhea, vomiting, sleepiness, and change in eating habits

Most of these reactions usually disappear within 1-2 days without treatment. As this vaccine has only been administered to a limited number of humans, there may be other yet unforeseen adverse events or reactions that may be associated with administration of this vaccine.

The aH5N1 vaccine has a good immunogenicity and a safety profile. The benefit-risk relationship for aH5N1 is positive for the prevention of infection from A/H5N1 virus.

When blood samples are taken, there is a risk of bruising at the injection site, soreness, possibly bleeding. Sometimes a person may become dizzy or faint for a short period of time. There is a rare possibility of infection or of nerve injury. Details of study procedures can be found in Section 3.

More detailed information about the known and expected benefits and risks and reasonably expected adverse events of the aH5N1 vaccine may be found in the Investigators' Brochure and the participant information leaflet.

2. OBJECTIVES

The purpose of this study is to assess the safety and immunogenicity of 6 different formulations including either 1.875, 3.75, or 7.5 µg HA of pandemic H5N1 influenza strain combined with either 0.125 mL or 0.25 mL MF59, in two IM injections administered three weeks apart.

2.1 Primary Objective(s)

Primary Safety Objective:

- To evaluate the safety in each study vaccine group from Day 1 through Day 387, by total population and by age cohort.

Primary Immunogenicity Objective:

- To assess by total population and by age cohort, the antibody responses to each of the study vaccines prior to (Day 1) and at 3 weeks after the first or second vaccination (Day 22 or Day 43), as measured by HI and MN assays.

2.2 Secondary Objective(s)

Secondary Immunogenicity Objectives:

- To evaluate in each study vaccine group, by total population and by age cohort, the persistence of antibody responses to the H5N1 vaccine strain 6 months after the second vaccination (Day 202) as measured by HI and MN assays.

2.3 Exploratory Objective(s)

- To further evaluate the antibody responses to seasonal, and/or homologous and/or heterologous pandemic influenza strain(s) by vaccine group on Days 1, 22, 43, and 202, as measured by HI, MN, or SRH assays (depending on availability of adequate sera and on assay availability).

3. STUDY DESIGN

3.1 Overview of Study Design

This randomized, observer blind, multi-center clinical trial evaluates the immunogenicity in healthy children ages 6 months to <9 years of 6 vaccine regimens utilizing 6 different formulations including either 1.875, 3.75, or 7.5 µg HA of pandemic H5N1 influenza strain combined with either 0.125 mL or 0.25 mL MF59, in two IM injections administered three weeks apart, in order to describe the possible impact of decreasing the quantities of antigen and/or adjuvant dosage. Levels of antibody persistence and the safety profile of each vaccine regimen will also be assessed.

A total number of 420 subjects will be enrolled to assure at least 150 evaluable subjects per age cohort.

Eligible subjects will be stratified by age at the time of enrollment into one of 2 age cohorts and within each age cohort will be randomly assigned (equally) to 1 of 6 study vaccine groups. Randomization will be equal (1:1:1:1:1:1) for each of 6 vaccine groups, and stratified by age cohort as follows: 6 months through <36 months of age, and 3 years through <9 years of age. Approximately 35 subjects will be randomized per vaccine group in each age cohort.

Subjects in each study vaccine group will be scheduled to receive 2 injections of aH5N1 vaccine 3 weeks apart.

The study groups are described in [Table 1](#).

Immunogenicity will be measured by HI and MN assays.

- Blood samples for serology assessments will be collected from each subject on Day 1 (before randomization), Day 22 (before vaccination), Day 43, and Day 202.
- Each subject will be followed for a period of 12 months after receipt of the second study vaccine. After informed consent is signed by the subject's parent(s) or LAR(s), and if applicable assent form is signed by the subject, eligibility is confirmed, and the Day 1 blood sample is collected, subjects will be randomized receive a single vaccination followed by a second vaccination after three weeks (Day 22). For all subjects, study participation includes a total of 4 clinic visits, 2 diary completion reminder calls, and 3 safety calls through the treatment and follow-up periods (a total duration of approximately 13 months).
- Treatment period (Day 1 through Day 43): 3 clinic visits and 2 reminder calls
- Follow-up period (Day 44 through Day 387): 1 clinic visit and 3 safety calls

Vaccine administration will be performed IM, anterolateral thigh for children ages < 2 years; deltoid for children ages \geq 2 years, unless insufficient deltoid mass. Each vaccine administration will be performed in an observer-blind manner (ie, efforts should be taken to shield the subject/parent(s)/LAR(s) and blinded study team members from the view of the vaccine administration). To maintain the observer-blind design of the study, the roles and responsibilities of “blinded” and “unblinded” team members will be defined and maintained. Safety assessments and study-related procedures and monitoring thereof must be performed by “blinded” team members.

After each vaccination, all subjects will remain under medical supervision at the study site for at least 30 minutes to be monitored and evaluated for AEs.

Subject Diary Cards will be provided to subjects for recording of local and systemic reactions for 7 consecutive days after each vaccination.

- From Day 1 through Day 7, and from Day 22 through Day 28, all solicited AEs, all unsolicited AEs (including SAEs, NOCDs, AEs leading to vaccine and/or study withdrawal, and AESIs), and associated concomitant medications for any of these events and vaccinations given within these periods will be recorded in the subject’s eCRFs.
- From Day 8 through Day 22 (before vaccination), and from Day 29 through Day 43 all unsolicited AEs (including SAEs, NOCDs, AEs leading to vaccine and/or study withdrawal, AESIs), solicited AEs that continue beyond Day 7 or Day 28 , respectively, and associated concomitant medications and all vaccinations given within these intervals will be recorded in the subject’s eCRF until the time of return to the clinic on Day 22, and Day 43,respectively in the subject’s eCRFs.

In the follow-up period (Day 44 through Day 387), only the following subset of unsolicited AEs and the associated concomitant medications/vaccinations will be collected and documented in the subject’s eCRFs: all SAEs, NOCDs, AEs leading to vaccine and/or study withdrawal, and AESIs (as described in [section 7.1](#) of the current protocol). These data will be captured by interviewing the subject’s parent(s)/LAR(s) and/or by reviewing the available medical records.

3.2 Study Period

Each subject should expect to participate in the study for approximately 12 months, from the time of enrolment through the last study visit.

3.3 Blinding Procedures

This is a phase 2, stratified, randomized, observer-blind, multicenter study. As such it is important to ensure that the subject and parent(s)/LAR(s) are not advised of the treatment assignment in this study.

Vaccine preparation and administration should be completed by the designated unblinded team members. Any other subject related assessments should be performed by the principal investigator (PI) and/or blinded staff members as applicable.

Except in the case of medical necessity, a subject's treatment should not be unblinded without the approval of the sponsor. In such instance of medical emergency, every effort should be made to contact the sponsor prior to unblinding. If unblinding should occur (by either accidental unblinding or emergency unblinding for a serious adverse event) prior to completion of the study, the investigator must promptly contact the sponsor and document the circumstances on the appropriate forms. Instructions regarding emergency unblinding will be provided to the investigator.

3.4 Data Collection

3.4.1 Data Collected from Subjects

The following data will be collected from each subject over the duration of their study participation:

- Informed Consent
- demographic information
- physical examination⁵ and clinical signs information
- adverse events
- relevant medical history
- relevant concomitant medications
- vaccination history (including influenza vaccination)
- serology results

⁵ A review of systems, ie, a structured interview for complaints for each organ system, will be used to guide a physical examination.

All data collected must only be identified using the sponsor's subject ID, as described in [section 5.1.4, Randomization](#).

3.4.2 Tools Used for Data Collection

Electronic Data Capture system and paper diary cards will be used to collect data for this study. Data will be collected in the Subject Diary Card by subject's parent(s) /LAR(s) or caregiver and recorded in electronic case report forms (eCRFs) by site staff.

Subject Diary Card

Paper diaries, hereafter referred to as Subject Diary Cards, will be the only source document allowed for solicited local and systemic adverse events (including body temperature measurements), starting after the initial 30-minute post-vaccination period at the clinic to 7 consecutive days after each vaccination. The following additional rules apply to documentation of safety information collected in the Subject Diary Card.

The Subject Diary Card will be completed by the parent(s) or LAR(s) or caregiver.

The investigator or delegated staff should monitor the Subject's Diary Card status throughout the study for compliance and any solicited local and systemic adverse events that were of concern to the subject.

1. No corrections or additions to the information recorded by the parent(s)/LAR(s)/caregiver within the Subject Diary Card will be allowed after it is delivered to the site.
2. Any blank or illegible fields on the Subject Diary Card must be described as missing, unknown or not done in the eCRF.

The following additional rules apply to documentation of Subject Diary Card information collected in the eCRFs:

- The site must enter all readable entries in the Subject Diary Card into the eCRF, including those values that may be biologically implausible (eg, body temperature: 400°C).
- Any illegible or implausible data should be reviewed with the parent(s)/LAR(s)/caregiver. If an underlying solicited or unsolicited adverse event is described on review with the subject's parent(s)/LAR(s)/caregiver, this should be documented in the source document and reported as an unsolicited adverse event in the adverse event eCRF (eg, if the subject's parent(s)/LAR(s)/caregiver confirms a body temperature of 40°C on the day in which body temperature:

400°C was written into his/her Subject Diary Card, this fever of 40°C should be recorded in the adverse event eCRF). No correction should be made on diary card.

- Any newly described safety information (including a solicited adverse event) must not be written into the Subject Diary Card, but must be documented in the source document as a verbally reported adverse event. Any adverse event reported in this fashion must be documented as an unsolicited adverse event and therefore entered on the adverse event eCRF.

Case Report Forms

This study utilizes eCRFs to collect study-related data from each subject. A qualified site staff member(s) is required to enter subject data in the eCRFs in English based on the medical information available in each subject's source record.

Data should be entered into the eCRF in a timely fashion following each subject's clinic visit, study procedure, or phone call. Each subject's eCRF casebook will be compared with the subject's source records by a sponsor-approved study monitor (or delegate) over the duration of the study in order to ensure data collection accuracy.

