6.3 Exclusions of Individual Values for Safety Analysis

Some local and systemic AEs will be directly measured by the subject and will not be subject to a reconciliation process, even if they are biologically implausible.

Therefore, these implausible measurements will be removed from the analysis but included in listings. Implausible measurements are summarized in the table below:

Table 2 Implausible Solicited Adverse Events

| Parameter | Implausible measurements |
|------------------|---|
| Body temperature | $\leq 33^{\circ}\text{C}$ or $\geq 42^{\circ}\text{C}$ |
| Erythema | For subjects ≥ 6 years: ≥ 900 mm and for subjects < 6 years: ≥ 450 mm Measurements < 0 mm |
| Induration | For subjects ≥ 6 years: ≥ 500 mm and for subjects < 6 years: ≥ 250 mm Measurements < 0 mm |
| Ecchymosis | For subjects ≥ 6 years: ≥ 500 mm and for subjects < 6 years: ≥ 250 mm Measurements < 0 mm |

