8.2 Handling of Dropouts, Missing Data

The distribution of subjects with reasons for missing immunogenicity values will be described by vaccine group. Key baseline characteristics, such as age and country, will be compared between the subjects with immunogenicity values and those who have missing data.

For immunogenicity data, it may be reasonable to consider missing immunogenicity values as missing completely at random (MCAR), i.e., not informative. Therefore, the immunogenicity analysis will comprise a complete case analysis only, without introducing any bias. Additional sensitivity analysis will be considered if the percentage of subjects with missing data is more than 10%.

Solicited AEs are collected using diaries from Day 1 to Day 7 post-vaccination. If the data have not been recorded for all 7 days, the assessment is considered missing and excluded from analysis. In case, at least one day is filled in but other days are missing the presence or absence of the event will be based on the available data. If more than 10% of the subjects have incomplete diary data, additional tables for solicited adverse events will be created based on complete diary card data. The number of days and number of subjects with missing data will be tabulated by vaccine group.

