Any solicited AE presence is defined as at least one day recorded a presence of a local or a systemic AE. No solicited AE is defined as for all days ‘No’ for all pre-defined solicited AEs. Same convention is used considering local and systemic events separate.

The use of analgesics/antipyretics will be considered as a separate category under “other”.

Solicited local adverse events, maximum event severity by event and interval

The **maximum event severity** will be defined if there is at least one plausible non- missing observation (excluding “Not done/unknown” and implausible values) within this time interval.

Statistical Analysis Plan, Protocol Number V87_30

06 MAY 2022 Final Version 1.0

Each subject's data will be aggregated across the time points of the interval and summarized according to the maximal severity observed for each local AE, followed by a summary across subjects for each vaccine. Subjects without any solicited AEs in the interval, i.e., missing values at each of the requested time points, will be removed from the denominator.

The time intervals will be 30 minutes, Day 1 to Day 7, Day 1 to Day 3 and Day 4 to Day 7. A summary tables will be created with the frequency using only any and severe events.

Solicited systemic adverse events, maximum event severity by event and interval

The analysis on the maximum severity of the systemic adverse events will be done along the same methods as for the local adverse events.

Number of days with solicited adverse events

The number of days with the AE is defined irrespective of severity. If a solicited AE continues beyond day 7 the period after day 7 is added.

The frequency distribution of the number of days will be provided in a summary table by vaccine and by AE.

Daily reports of solicited adverse event

For each of the time points only subjects with at least one plausible observation (i.e., any non-missing values but excluding "Not done/unknown" and implausible values) for the solicited AE in the interval of interest will be considered. Subjects without plausible data (i.e. missing values or reported as "Not done/unknown" and implausible values) will be removed from the denominator to prevent a downward bias (towards zero). Data collected will be summarized (frequencies and percentages of subjects) by vaccine group, solicited AE, vaccination number and time point.

Time of first onset of solicited adverse events

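### Parent-confirmed solicited reactions filed as unsolicited drop out of the primary solicited endpoint, and the child is scored 'none' when all remaining valid diary entries show none

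*Protocol*

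**What the plan says.** **Collection (Protocol 3.4.2).** After the 30-minute clinic observation, the paper diary "will be the only source document allowed for solicited local and systemic adverse events". Nothing may be corrected or added once the card reaches the site. Three kinds of problem are then handled as follows:

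- Blank or illegible: "Any blank or illegible fields on the Subject Diary Card must be described as missing, unknown or not done in the eCRF".
- Implausible or illegible, and the parent confirms an underlying event on review: the diary stays as it is, and the event is "reported as an unsolicited adverse event in the adverse event eCRF". The protocol's own example is a 40 °C fever written as 400 °C.
- Not on the card at all, and first described verbally: "Any adverse event reported in this fashion must be documented as an unsolicited adverse event and therefore entered on the adverse event eCRF".

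**Analysis (SAP).** Section 6.3 treats temperatures of 42 °C or more (among other values) as implausible and says "these implausible measurements will be removed from the analysis but included in listings". Section 8.2 says of diaries: "If the data have not been recorded for all 7 days, the assessment is considered missing and excluded from analysis". It then adds that, where at least one day is filled in, "the presence or absence of the event will be based on the available data". Section 13.2 says that maximum severity "will be defined if there is at least one plausible non- missing observation", and removes a child from an interval's denominator only when no valid observation exists in it. For the overall summary, 13.2 defines having no solicited AE as a 'No' on all days for all solicited events.

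**Endpoints (Protocol 8.1.1.1).** The percentage of children with solicited AEs (30 minutes, Days 1-3, 4-7 and 1-7 after each vaccination) and the percentage with unsolicited AEs within 21 days of each vaccination are both primary safety endpoints.

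**The concern.** Read in sequence, these rules separate what the site knows from what the solicited tables show. The event is on the AE form, dated and confirmed, while the solicited tables are built from valid diary entries alone. For a one-day recording error in an otherwise quiet week, the remaining days read 'none', and so does the child.

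The unsolicited tables are not an equivalent home for the event:

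- **Causality.** Protocol 7.1.3 treats all Day 1-7 solicited AEs as adverse drug reactions. An unsolicited AE depends on the investigator's judgement.
- **Severity.** SAP Table 3 grades fever by measured temperature. The AE form grades by limitation of daily activity, so a 40 °C fever need not appear as severe.
- **Tabulation.** The maximum-temperature table in SAP 13.2 draws on solicited data and misses the event. The one planned summary that combines solicited and unsolicited events (SAP 13.3) is for registry posting and is limited to non-serious events in more than 5% of subjects.

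The study is descriptive, so these percentages are themselves the reactogenicity result for each formulation. SAP 13.2 recognises the risk of a downward bias and guards against it for intervals with no valid data. It does not guard against it where the interval is partly valid and the event is known.

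**Working it through.** The plan states no figure on this point, so there is none to reproduce. The check applies the SAP rule to example diaries and then sizes the effect of one child.

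**Rule applied, per solicited event and interval:** drop implausible and missing days. If no day is left, the child is out of the denominator. If any remaining day shows the event, the child has the event at the maximum remaining severity. Otherwise the child is 'none'.

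In each row below, the event occurred and was recorded on the AE form as unsolicited.

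| Diary pattern | Days 1-3 | Days 4-7 | Days 1-7 |
|---|---|---|---|
| Day 1 unusable, six days 'none' | none | none | none |
| 'None' ticked on all seven days, event reported verbally later | none | none | none |
| Day 1 unusable, event validly recorded on Day 2, rest 'none' | event | none | event |
| Days 1-3 unusable, Days 4-7 'none' | out | none | none |
| All seven days unusable | out | out | out |

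The protocol's example falls in the first row if the other six readings are normal: 400 °C is at or above 42 °C, so it is removed, six valid readings remain, and fever is 'none'. If another day has a valid 38.2 °C (an illustrative value), the child falls in the third row. Fever is then present but Grade 1 (38.0-38.9 °C in SAP Table 3), where the confirmed 40 °C would be Grade 3.

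**Reading of SAP 8.2.** Its first diary sentence could mean that any gap in the seven days makes the assessment missing. The sentence after it, on at least one completed day, supports the reading used above: missing only if no day is recorded. On the stricter reading, the child in the first row leaves the denominator instead. The known event is still not counted.

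**Overall summary.** A child with one unusable day and otherwise 'No' is without an event under SAP 8.2 (available data), but does not literally meet the SAP 13.2 definition ('No' on all days). The two sections do not settle how this child is classed there.

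**Size.** Inputs: about 35 children per arm and age cohort and about 70 per arm (Protocol 3.1 and Table 6.1). Each child scored 'none' instead of 'event' lowers the percentage by 1/n:

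- 1/35 = 2.9 percentage points
- 1/70 = 1.4 percentage points

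The documents give no event rates. Assuming a true rate of 20% for illustration:

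| n | True | 1 re-filed | 2 re-filed | 3 re-filed |
|---|---|---|---|---|
| 35 | 7/35 = 20.0% | 6/35 = 17.1% | 5/35 = 14.3% | 4/35 = 11.4% |
| 70 | 14/70 = 20.0% | 13/70 = 18.6% | 12/70 = 17.1% | 11/70 = 15.7% |

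A child who leaves the denominator also lowers the rate, slightly less: 7/35 = 20.0% becomes 6/34 = 17.6%.

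**The case against.** **The routing is deliberate.** A single prospective source keeps diary entries apart from recall, and that is a legitimate design choice. This stands, and it is why the diary-only tables should not be altered.

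**The event is not lost.** It counts in the other primary safety endpoint, unsolicited AEs within 21 days. It appears in the tables by system organ class and preferred term and in the listings, whatever the relatedness, and missing relatedness counts as related (SAP 8.7). Raw implausible values are listed too. All of this stands, so a reader should not infer that the reaction disappears from safety reporting. It disappears only from the solicited rates.

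**Partial safeguards exist.** SAP 13.1.1 tabulates days with valid data per solicited event, and SAP 8.2 adds complete-diary tables if more than 10% of subjects have incomplete diaries. These show how much is missing but restore no event. A diary with 'none' ticked on every day counts as complete.

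**Nothing shows that the effect is large or differs by arm.** This is correct. The documents give no frequency, and the study is observer-blind.

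**A stronger reading is tempting:** that every such child is counted as event-free in the primary solicited endpoint. The documents do not support it. Blank and illegible fields are missing, not 'none'. A child with no valid entry in an interval leaves its denominator. A child with the event validly recorded on another day of the interval is counted. The 30-minute interval is observed by site staff and does not depend on the diary. The classification in the overall summary is unsettled.

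**Conclusion.** The point holds in a conditional form. A solicited reaction confirmed after an implausible or illegible entry, or first reported verbally, is recorded only as unsolicited and is not counted in the primary solicited endpoint. In the diary-based per-event tables the child is scored 'none' if all valid entries in the interval show none, and may be scored at too low a maximum severity if a milder valid entry exists.

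The omission works in one direction: it can lower the solicited rates, fever and the maximum-temperature table included, but cannot raise them. Its size is 2.9 points per child scored 'none' per arm and age cohort, or 1.4 points per arm, assuming the planned 35 and 70 children; with fewer evaluable diaries each child weighs slightly more. For a rare event such as fever of 40 °C or more, one child can be the difference between 0 and 1 case. The number of children affected is unknown, so material bias is not shown, and neither is any distortion of the comparison between formulations. The case for change is that the information is already in the database and the remedy is cheap.

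**What to change.** 1. **Leave unchanged** the diary rule in Protocol 3.4.2 and the diary-only tables. Removing affected children from the diary-only denominator is not a remedy: in the illustration it moves 6/35 = 17.1% only to 6/34 = 17.6%, still below 20.0%, and makes the diary table depend on recalled data.

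2. **Add to SAP 13.2 one supplementary solicited table**, by event, interval and maximum severity, shown beside the diary-only table. Count diary events plus AE-eCRF records that match a solicited term with onset in the seven days after either vaccination (Days 1-7 or 22-28). Include events reported verbally after 'none' was ticked. Grade fever by the confirmed temperature where it is available. Count each child once per event and interval, because solicited events continuing past Day 7 are already on both forms. State the denominator; a child counted through the AE form must be in it.

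3. **Reconcile** the 'No' on all days definition in SAP 13.2 with the available-data rule in SAP 8.2, so that a child with some missing days and otherwise 'No' has one classification in the overall summary.

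The cost is SAP wording, a map from the solicited terms to MedDRA preferred terms, and one extra table. The downside is small: the new table mixes prospective and recalled data, which is why it sits beside the diary-only table and does not replace it.
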